Figure 16-1	Physician Global Assessment of Autoinflammatory Disease Activity	102
Figure 16-2	Physician's Severity Assessment of Autoinflammatory Disease Signs and Symptoms	103
Figure 16-3	Patients Global Assessment of Disease Activity	104

List of abbreviations

AE	Adverse Event
AIDS	Acquired Immune Deficiency Syndrome
ALB	Albumin
ALP	Alkaline Phosphatase
ALT	Alanine Aminotransferase
ANC	Absolute Neutrophil Count
anti-HBc	Hepatitis B core antibody
APTT	Activated Partial Thromboplastin Time
AST	Aspartate Aminotransferase

Commercially Confidential Information

b.i.d.	bis in die / twice a day
BMI	Body Mass Index
BP	Blood Pressure
BUN	Blood Urea Nitrogen
CAPS	Cryopyrin-Associated Periodic Syndromes
CINCA	Chronic, Infantile, Neurological, Cutaneous and Articular Syndrome
CK	Creatine Kinase
CKD-EPI	Chronic Kidney Disease Epidemiology Collaboration
ClinRO	Clinician Reported Outcomes

Commercially Confidential Information

CMO & PS	Chief Medical Office and Patient Safety
CO	Country Organization
COA	Clinical Outcome Assessment
CRO	Contract Research Organization
CSR	Clinical Study Report
CTCAE	Common Terminology Criteria for Adverse Events
Ctrough	Trough concentration
CV	Coefficient of Variation
CXCL10	C-X-C motif chemokine ligand 10
CYP	Cytochrome P450
DDE	Direct Data Entry
DDI	Drug-Drug Interaction
DNA	Deoxyribonucleic acid
ECG	Electrocardiogram
eCRF	Electronic Case Report/Record Form
EDC	Electronic Data Capture
eGFR	Estimated Glomerular Filtration Rate
eSource	Electronic Source

FCAS	Familial Cold Autoinflammatory Syndrome
FIH	First in Human
FMF	Familial Mediterranean Fever
FSH	Follicle Stimulating Hormone
G-GT	Gamma-Glutamyl Transferase
GCP	Good Clinical Practice
GLP	Good Laboratory Practice
h	Hour
HBsAg	Hepatitis B surface antigen
hCG	Human Serum Chorionic Gonadotropin
HCV	Hepatitis C Virus
HIV	Human Immunodeficiency Virus

Commercially Confidential Information

IB	Investigator's Brochure
IC50	Half maximal inhibitory concentration
IC90	Concentration required to achieve 90% of inhibition
ICF	Informed Consent Form
ICH	International Council for Harmonization of Technical Requirements for Pharmaceuticals for Human Use
IEC	Independent Ethics Committee
IFN- γ	Interferon-gamma
IL-1	Interleukin-1
IL-18	Interleukin-18
IL-18BP	IL-18 binding protein
IL-1 β	Interleukin-1beta
IL-6	Interleukin-6
IN	Investigator Notification
INR	International Normalized Ratio
IRB/IEC	Institutional Review Board / Independent Ethics Committee
IUD	Intrauterine Device
IUS	Intrauterine System

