4.6.6 Potential risk and recommended treatment of infection

As with any immune-modulating compound, there is a theoretical risk of immune system impairment which might increase risk of infection in treated participants. However, DFV890 is not expected to elicit broad immune suppression. Commercially Confidential Information

. To mitigate potential risks of immune suppression and infection in this study, exclusion criteria include other immune suppressive treatments administered 28 days or 5 half-lives, whichever is longer, prior to screening cold challenge, or concurrent use thereof. Participants will also be excluded with known or suspected immunodeficiency state or evidence of active or latent, serious bacterial, fungal or viral infections. See [Section 5.2](#).

In response to the COVID-19 pandemic site-specific procedures should be implemented to minimize COVID-19 infection risks for participants and site staff as per local guidance. These documents may cover, but are not limited to, local COVID-19 testing, infection prevention/control, hygiene and social distancing measures.

Investigator must instruct participants to contact the investigator immediately if the participants develop any symptoms and/or signs of infection (e.g. fever, loss of smell, loss of taste, muscle aches, persistent or productive cough, abdominal pain, vomiting, nausea, shortness of breath, dysuria and/or diarrhea).

In the event of an infection, investigators should consider early treatment with specific antimicrobial therapy based on clinical diagnosis or suspicion thereof (e.g. anti-viral treatment for herpes simplex or zoster or SARS-CoV-2) in consultation with infectious disease experts, as appropriate.

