5.2 Exclusion criteria

Participants meeting any of the following criteria are not eligible for inclusion in this study.

1. Commercially Confidential Information

2. Anti-rejection and/or immunomodulatory drugs must be discontinued (see [Section 6.2.2](#)):
 - Anakinra at least 1 day prior to the screening cold challenge and until study completion
 - Canakinumab and rilonacept at least 3 half-lives prior to the screening cold challenge, at least 5 half-lives prior to Day 1 and until study completion
 - Other anti-rejection/immune modulatory therapies at least 3 half-lives prior to screening cold challenge, at least 5 half-lives prior to Day 1 and until study completion
 - Ad hoc use of anakinra is permitted for the interval between the screening cold challenge and Day 1, if it can be discontinued at least 5 half-lives prior to Day 1
 - Ad hoc use of paracetamol and non-steroidal anti-inflammatory drugs (NSAIDs, as per local regulations/practice) is permitted for symptomatic relief
3. Participants currently being treated with drugs known to be strong or moderate inducers of isoenzyme CYP2C9 and/or strong inhibitors of CYP2C9 and/or strong inducers of

cytochrome P450, family 3, subfamily A (CYP3A) or dual strong or moderate inhibitors of CYP2C9/CYP3A (see list of prohibited drugs [Table 6-3](#)) and the treatment cannot be discontinued or switched to a different medication by 5 half-lives or 1 week (whichever is longer) prior to Day 1 and for the duration of the study.

4. Participation in any other investigational trials within 5 half-lives or within 30 days of screening (e.g. investigational small molecules) or until the expected PD effect has returned to baseline (e.g. investigational biologics), whichever is longer; or longer if required by local regulations with the exception of treatment with anakinra, canakinumab, rilonacept and/or other investigational IL-1/NLRP3 binding or blocking therapy.
5. Participants with innate (e.g. Toll-like receptor (TLR) immunodeficiencies, defects in interferon-gamma (IFN- γ) signaling) or acquired immune deficiencies (e.g. AIDS).
6. Presence of human immunodeficiency virus (HIV) infection, hepatitis B surface antigen (HBsAg) or hepatitis B core antibody (anti-HBc), or hepatitis C antibodies at Screening.
7. Participants who have undergone solid organ or stem cell transplantation.
8. Live vaccines within 4 weeks of Day 1.

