^x Assessment to be recorded in the clinical database or received electronically from a vendor

^s Assessment to be recorded in the source documentation only

¹ Visit Numbers given for internal programming purpose only

² Assessments to be conducted prior to first dose

³ Assessments to be conducted prior to the morning dose

⁴ Admission can be delayed with a maximum of one day and treatment hence prolonged to with one day. This option should only be used under exceptional circumstances

⁵ To confirm eligibility, available historical CYP2C9 genotyping results confirming the absence of the CYP2C9*3/*3 variant previously issued in frame of this study are acceptable for re-screened participants

⁶ Participant domiciliation may be prolonged at the discretion of the investigator and patient

⁷ The start of the cold challenge is at 1 h and the duration is 45 minutes. The screening cold challenge should be initiated 1 h after meal and treatment cold challenge 1 h after treatment administration.

⁸ Where possible, white cell count should be included as part of hematology sampling, rather than collecting a separate sample

⁹ Commercially Confidential Information

¹⁰ To be collected at 0 h prior to morning dose and 12 h after previous evening dose the day before

¹¹ To be collected at 1 h postdose, prior to initiation of cold challenge

¹² Commercially Confidential Information

¹³

¹⁴ Also applicable in case of early discontinuation

¹⁵ 30 days after last dose

¹⁶ Vital signs to be collected every 10 minutes during the cold challenge and at the end of the cold challenge

¹⁷ The Physician Global Assessment of Autoinflammatory Disease Activity conducted at the Screening Cold Challenge Admission visit must capture evidence of disease flare (> minimal) occurring during the screening period

¹⁸ The screening cold challenge can be conducted any time during the screening period (the visits "Admission", "Screening Cold Challenge" and "Discharge" must occur on 3 consecutive days), provided that Day 1 is conducted within 6 months (and within 12 months for participants with a historical screening cold challenge prior to protocol amendment 04) of the Screening visit

¹⁹ Participants can be admitted to the Screening Cold Challenge visit only when all eligibility criteria are confirmed, except inclusion criterion 8 which is assessed during the screening cold challenge

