8.1.1 Eligibility screening

8.1.1.1 Hepatitis screen, HIV screen

All participants will be screened for Hepatitis B surface antigen (HBsAg) and, if standard local practice, Hepatitis B core antigen (HBcAg). Screening for Hepatitis C will be based in Hepatitis C Virus (HCV) antibodies and if positive, HCV RNA levels should be determined.

Evaluation for HIV seropositivity will be performed, and, if positive, confirmation by a second technique available at the laboratory site; e.g. Western blot. Appropriate counseling will be made available by the Investigator in the event of a positive confirmatory test. Notification of state and federal authorities, as required by law, will be the responsibility of the Investigator.

Samples will be collected and processed according to local procedures and analyzed at the local laboratory.

Hepatitis and HIV Screen may be repeated according to the investigator's discretion, if performed more than 6 months prior to Day 1.

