11.3 Site monitoring

Before study initiation, at a site initiation visit or at an investigator's meeting, a Novartis representative will review the protocol and data capture requirements (i.e. eSource Direct Data Entry (DDE) or eCRFs) with the investigators and their staff. During the study, Novartis employs several methods of ensuring protocol and GCP compliance and the quality/integrity of the sites' data. The field monitor will visit the site to check the completeness of participant records, the accuracy of data capture / data entry, the adherence to the protocol and to GCP, the progress of enrollment, and to ensure that study treatment is being stored, dispensed, and accounted for according to specifications. Key study personnel must be available to assist the field monitor during these visits. Continuous remote monitoring of each site's data may be performed by a centralized Novartis Clinical Research Associate organization. Additionally, a central analytics organization may analyze data & identify risks & trends for site operational parameters, and provide reports to Novartis clinical teams to assist with trial oversight.

The investigator must maintain source documents for each participant in the study, consisting of case and visit notes (hospital or clinic medical records) containing demographic and medical information, laboratory data, electrocardiograms, and the results of any other tests or assessments. All information on eCRFs must be traceable to these source documents in the participant's file. The investigator must also keep the original ICF signed by the participant (a signed copy is given to the participant).

The investigator must give the monitor access to all relevant source documents to confirm their consistency with the data capture and/or data entry. Novartis monitoring standards require full verification for the presence of informed consent, adherence to the inclusion/exclusion criteria, documentation of SAEs, and of data that will be used for all primary variables. Additional checks of the consistency of the source data with the eCRFs are performed according

to the study-specific monitoring plan. No information in source documents about the identity of the participants will be disclosed.

12 Data analysis and statistical methods

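### Exclusion criterion 6 bars anyone with hepatitis B core antibody, but the screening section names core antigen, and only where local practice includes it

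*Protocol*

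**What the plan says.** The eligibility rule is in Protocol section 5.2, criterion 6: "Presence of human immunodeficiency virus (HIV) infection, hepatitis B surface antigen (HBsAg) or hepatitis B core antibody (anti-HBc), or hepatitis C antibodies at Screening". Meeting any one exclusion criterion makes a participant ineligible. The key exclusion criteria in the protocol summary repeat the rule, again without a condition.

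The procedure is in Protocol section 8.1.1.1: "All participants will be screened for Hepatitis B surface antigen (HBsAg) and, if standard local practice, Hepatitis B core antigen (HBcAg". The same section has hepatitis C antibody and HIV serology evaluated without a local-practice condition, and sends samples to the local laboratory under local procedures.

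Three other places bear on the point:

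- Table 8-1 has a single row for the hepatitis and HIV screen. It names no marker and carries the code S, defined under the table as "Assessment to be recorded in the source documentation only".
- Footnote 19 to Table 8-1 allows admission to the screening cold challenge "only when all eligibility criteria are confirmed, except inclusion criterion 8 which is assessed during the screening cold challenge".
- Section 11.3 requires the monitor to verify fully, among other things, "adherence to the inclusion/exclusion criteria".

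**The concern.** An eligibility criterion can be applied only if the measurement it depends on is taken. Here the criterion depends on anti-HBc, while the section that tells sites what to measure names a different marker and makes it optional. A site where core testing is not routine can carry out section 8.1.1.1 in full and still have no result for that part of criterion 6.

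The consequence would be the enrolment and dosing of someone the protocol says is ineligible, and different handling of the same person at different sites. Section 4.6.6 gives as one mitigation of infection risk the exclusion of participants with "evidence of active or latent, serious bacterial, fungal or viral infections", and refers to section 5.2 for the criteria that do this. Criterion 6 is one of them.

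**Working it through.** There is no arithmetic to reproduce. The check compares each component of criterion 6 with what section 8.1.1.1 orders.

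| Component of criterion 6 | Condition in criterion 6 | Ordered by section 8.1.1.1 | Match |
|---|---|---|---|
| HIV infection | none | yes, with a confirmatory test if positive | yes |
| HBsAg | none | yes, in all participants | yes |
| Anti-HBc (core antibody) | none | no; core antigen instead, subject to local practice | no |
| Hepatitis C antibody | none | yes, with RNA if positive | yes |

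One of the four components has no matching mandatory test. For hepatitis C, the added RNA measurement has no stated role in eligibility, since criterion 6 excludes on antibody alone. The antibody is still measured in everyone, so that component is assessed.

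**Is the mismatch only a wording slip?** The list of abbreviations defines anti-HBc as "Hepatitis B core antibody" and has no entry for HBcAg, which suggests that antigen was written for antibody. Making that substitution in section 8.1.1.1 removes the difference in marker. The local-practice condition stays, and criterion 6 has no such condition. The inconsistency therefore survives the most favourable reading.

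**Does another passage order the test?**

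- The Table 8-1 row is generic. Footnote 23 lets the investigator repeat the screen if it was done more than 6 months before Day 1, but adds no marker.
- Table 8-3 lists hematology, chemistry, urinalysis, coagulation and pregnancy tests, and no hepatitis serology.
- Footnote 19 requires criterion 6 to be confirmed before the screening cold challenge, but names no test.
- Anti-HBc appears in the abbreviation list, the protocol summary and section 5.2, and nowhere in the description of procedures.

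**Would a missing result be visible?** The Inclusion/Exclusion row of Table 8-1 is coded X, so the eligibility decision reaches the clinical database. The hepatitis screen is coded S, so the database does not record which hepatitis B markers were run. A participant could be recorded as eligible without an anti-HBc result, and only source review would show it.

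**How many participants?** Those who could lack the result are the participants at sites where core testing is not local practice, or where core antigen is read literally. That is between 0 and all enrolled: about 6, and not more than 10 (section 5). The documents give neither site practice nor anti-HBc prevalence, so the number wrongly enrolled cannot be estimated.

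**Does it reach the analysis?** No. The sample size in section 12.8.1 does not depend on hepatitis status. The visible rows of SAP Table 4-1 exclude participants from the PD analysis set, which the primary analysis uses, for missing consent or for failing the white cell count criterion. Criterion 6 is not among them.

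**The case against.** The strongest reply is that the criterion still binds. Section 5.2 makes anyone meeting it ineligible, footnote 19 bars admission to the cold challenge until it is confirmed, and section 8.1.1.1 neither forbids an anti-HBc test nor claims to be a complete list. On this view, wrong enrolment requires a site to follow one section and disregard two others, and the monitor's full check of eligibility should then catch it.

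Much of this is fair, and it limits how likely the error is. It does not remove the contradiction. Footnote 19 demands a confirmation for which no passage supplies the test. A monitor working from section 8.1.1.1 could accept a missing core result as compliant, while one working from section 5.2 could call it a deviation. The backstop is therefore affected by the same ambiguity.

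A second reply is that the safety consequence should not be overstated, and that stands. No passage says that an HBsAg-negative, anti-HBc-positive person has a latent serious infection. The link to section 4.6.6 rests only on that section's reference to the exclusion criteria. Other safeguards remain, including criterion 9 on active or chronic infection, criterion 13 on liver tests, and a short planned exposure of seven doses (3 days × 2, plus 1).

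**Conclusion.** The concern holds. Criterion 6 and its line in the summary exclude on anti-HBc without condition, while section 8.1.1.1 requires only HBsAg in everyone and makes a differently named core marker depend on local practice. Followed as written, section 8.1.1.1 can lead to a wrong eligibility decision.

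The reach is limited to one of the criterion's four components and to a trial of at most 10 participants, with two partial backstops in footnote 19 and monitoring. The conclusion assumes only that at least one site might follow section 8.1.1.1 literally or not test core markers routinely. It assumes nothing about prevalence. It is worth correcting because the criterion concerns who may be dosed, but it does not bear on the validity of the primary result.

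**What to change.** Reconcile three places: section 5.2 criterion 6, the matching line in the protocol summary, and section 8.1.1.1. All three should name the same hepatitis B core marker and state alike whether it is tested in every participant. The sponsor's clinical team must decide which passage governs; this review takes no position on that. The hepatitis and HIV row of Table 8-1 should then refer to the reconciled marker list.

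The cost is wording in three places and one cross-reference. If the procedure is brought into line with the criterion, there may be one more serology result per participant and possibly an additional screen failure. If the criterion is the passage that changes, no test is added.

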8.1.1.2 Tuberculosis (TB) testing

In order to evaluate the tuberculosis (TB) status of the participants, a TB test should be performed at Screening as per local regulations/guidelines using one or both of the following methods:

- QuantiFERON®-TB assay
- Tuberculin skin testing

Samples will be collected and processed according to local procedures and analyzed at the local laboratory. Negative test results from the previous 3 months may be used if available.

Tuberculosis test may be repeated according to the investigator's discretion, if performed more than 6 months prior to Day 1.

Any significant findings will be recorded in the Relevant medical history/Current medical conditions section of the eCRF as necessary.

8.1.2 Information to be collected on screening failures

Participants who sign an informed consent form and subsequently found to be ineligible will be considered a screen failure. This applies also to participants who are considered screen failures after the screening cold challenge. The reason for screen failure should be entered on the

applicable eCRF. The demographic information, informed consent, and Inclusion/Exclusion pages must also be completed for screen failure participants. Additional data may be entered to support the eligibility decision, such as – but not limited to – medical history, relevant prior and concomitant medications, hematology, clinical chemistry. SAEs will also be collected for screen failed participants (see SAE section ([Section 10.1.3](#)) for reporting details).

Participants who sign an informed consent and are considered eligible but fail to be started on treatment for any reason will be considered an early terminator. The reason for early termination should be captured on the appropriate disposition eCRF.

8.2 Participant demographics/other baseline characteristics

Demographic information

Country-specific regulations should be considered for the collection of demographic and baseline characteristics in alignment with eCRF. Participant race and ethnicity are collected and analyzed to identify variations in safety or efficacy due to these factors as well as to assess the diversity of the study population as required by Health Authorities.

Participant demographics: year of birth (age), sex, race, predominant ethnicity (if permitted), child-bearing potential (women only), relevant medical history/current medical conditions (until date of signature of informed consent), specific NLRP3 mutation (if available) and nicotine use will be recorded in the eCRF. Where possible, the diagnosis and not symptoms should be recorded. Vaccination status (12 months prior to the participant's consent until the Study completion visit) should be recorded as part of the collection of medical history/current medical conditions.

All prescription medications, over-the-counter drugs and significant non-drug therapies prior to the start of the study must be documented. See the protocol [Section 6.2.1](#) Concomitant Therapy for further details on what information must be recorded on the appropriate page of the eCRF.

FCAS medical history and diagnosis

The following should be recorded in the participants medical records

- Molecular diagnosis of NLRP3 mutations
- Absence of L353P mutation
- Presence of mutation with documented responsiveness to DFV890 in *ex vivo* testing if available
- Clear documentation of use of and response to previous treatment therapeutics targeting the IL-1 β pathway if available
- Presence of active disease following discontinuation of current treatment as outlined in [Section 5.1](#).
- Any available documentation of previous medical assessments (e.g. auditory brainstem response, neurological and ophthalmological assessments) to document absence of organ damage and/or amyloidosis

